1.0 Introduction

The coflex® Interlaminar Technology - manufactured by Paradigm Spine - is intended for use as a permanent implant between the lamina of 1 or 2 lumbar motion segments in the treatment of moderate to severe lumbar spinal stenosis. The device is specifically designed to provide stabilization without fusion in cases of stenosis with or without facet joint hypertrophy, subarticular recess stenosis or foraminal stenosis. It is restricted for use to one or two levels in the region of L1 – L5.

The height of the neuroforamen is maintained and the facet joints will be relieved. By this a further destruction is prevented. Unlike conventional stabilization methods as for example spinal fusion, the function of the segment will be maintained and adjacent structures will be effectively protected.

Possible risks, which could occur after implantation of the coflex® Interlaminar Technology are breakage of the implant, displacement of the implant, pain which is caused by the implant, infections, bleedings and hematoma. The benefit of the study lies in the fact that first-time retrospective data is raised for potential improvement regarding therapy of lumbar back pain with the treatment of the lumbar spinal stenosis, which, in the future, can lead to an improvement of the therapy.

In this study, Paradigm Spine will retrospectively collect clinical and radiographic data for patients treated with the coflex® Interlaminar Technology during normal conditions of use. This data will provide evidence to support publications and marketing.

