2.0 Study Purpose

2.1 Primary Objective

- To assess the operative details and safety outcomes associated with the use of the coflex device
- To assess post-operative adverse events
- To assess post-operative follow-up duration

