4.1 Endpoints

Patient reported outcomes will be assessed as part of the primary objective.

Clinical and radiologic outcomes, demographics and risk factors will be assessed as part of the secondary objectives. These include, but are not limited to:

- Age
- Gender
- Ethnicity
- Height and Weight
- BMI
- Narcotics use
- Comorbidities
- Bone Density
- Presenting Symptoms
- Radiologic Data (Anterior/Posterior and Flexion/Extension films, as well as, MRI and/or CT Scan used to confirm diagnosis of spinal stenosis)
- Operative Data
- Intra-Operative Complications
- Return to Work
- Changes in Activities of Daily Living (ADL)
- Patient Satisfaction
- Repeat Surgery Details

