5.0 Statistical Analysis

5.1 General Information

All continuous outcome measurements at follow-up time points will be compared to baseline values using a t-test for superiority. Categorical outcome measurements will be compared using a Fisher's exact test for superiority. Statistical significance for these analyses will be demonstrated with a p-value less than 0.05.

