5.3 Secondary Endpoints

The clinical outcomes will be summarized; however, since the collection of these measures is not standard of care, this data will only be collected as available. In addition, data will be used to analyze the association between coflex® Interlaminar Technology use and outcomes with age, ethnicity, race, workers' compensation, smoking status, and gender. New and/or worsening complications will be summarized.

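### Adverse events are a primary objective, but the plan fixes no comparison for complications: 5.1 offers only an undirected superiority test, 5.3 only a summary, and neither bounds excess harm

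*Combined protocol and SAP*

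**What the plan says.** Section 2.1 lists three primary objectives. The first covers operative details and safety outcomes with the device; the second is "To assess post-operative adverse events". The title sets coflex against decompression with or without fusion, and section 4.0 collects patients from both sides of that comparison.

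Section 5.1 holds every inferential rule in the plan:

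- Continuous data: "All continuous outcome measurements at follow-up time points will be compared to baseline values using a t-test for superiority".
- Categorical data: "Categorical outcome measurements will be compared using a Fisher's exact test for superiority". Neither a baseline nor a comparison group is named.
- Threshold: "Statistical significance for these analyses will be demonstrated with a p-value less than 0.05".

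Section 5.2 does not mention complications. It analyses follow-up duration and secondary surgical interventions, framed as effectiveness. Section 5.3, under secondary endpoints, says: "New and/or worsening complications will be summarized". Section 4.1 lists "Intra-Operative Complications" among the items assessed under the secondary objectives. The plan gives no risk difference, confidence interval, safety margin, expected event rate or group size.

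**The concern.** Section 1.0 names risks that belong to the implant itself: "breakage of the implant, displacement of the implant, pain which is caused by the implant". Decompression without a device cannot produce these. Against decompression alone, therefore, the natural safety question is whether complications are more frequent with coflex, and by how much. Against fusion the documents give no expected direction, so the estimate should be open to either.

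A significance test framed as superiority answers neither form of the question. It returns a p-value, and when that value is above 0.05 it does not say how large an excess is still compatible with the data. Section 1.0 says the data will support publications and marketing. A safety table carrying only counts and p-values would leave readers of those publications unable to tell a well-supported absence of excess from an imprecise one.

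**Working it through.** **No figure to reproduce.** The plan states no power, event rate, margin or sample-size calculation. It gives a total of about 5000 patients from 50 sites (Protocol Summary) and the 0.05 threshold (5.1). All rates and splits below are assumptions.

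**Step 1: which rule governs complications?** Section 5.1 covers categorical outcomes and exempts none. Section 5.3 speaks of complications specifically but names no test. Three readings follow:

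| Reading | Consequence for excess harm |
|---|---|
| 5.1, one-sided towards benefit | Harm cannot be declared |
| 5.1, two-sided | Harm can be declared, but a non-significant result gives no bound |
| 5.3 only | No between-group estimate is promised |

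**Step 2: one-sided reading.** The rejection region holds only results with fewer events on coflex. At assumed true risks of 6% and 4%, the chance of any rejection is about 0.01% or less at the splits in Step 3, and any such rejection would favour coflex. Enlarging the study does not help.

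**Step 3: two-sided reading.** With *a* events among *n*₁ coflex patients and *b* among *n*₂ comparator patients, the exact power to show harm is

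Σ Bin(*a*; *n*₁, *p*₁) × Bin(*b*; *n*₂, *p*₂), summed over all (*a*, *b*) with two-sided Fisher p < 0.05 and *a*/*n*₁ > *b*/*n*₂.

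The splits (coflex : comparator) are:

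- 2500:2500, both comparators pooled.
- 1667:1667, one contrast when 5000 is divided equally among coflex, decompression alone and decompression with fusion (5000/3 ≈ 1667).
- 4000:500, one contrast when 4000 are coflex and each comparator has 500 (4000 + 500 + 500 = 5000).

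| Assumed risk, coflex v comparator | 2500:2500 | 1667:1667 | 4000:500 |
|---|---|---|---|
| 6% v 4%: power | 89% | 73% | 43% |
| 6% v 4%: missed | 11% | 27% | 57% |
| 2% v 1%: power | 81% | 62% | 29% |
| 1% v 0.5%: power | 48% | 31% | 11% |
| 1% v 0.5%: missed | 52% | 69% | 89% |

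In the other direction, 4% v 2% at 2500:2500 has 98.5% power. The miss rate is small for commoner events in balanced groups and large for rare events or a small group. Section 4.4.2 names individual types (dural tear, haematoma, fracture, nerve injury), so type-by-type tables may well involve low rates.

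**Step 4: what an interval would show.** The half-width is 1.96 × √(*p*₁(1−*p*₁)/*n*₁ + *p*₂(1−*p*₂)/*n*₂). At 6% v 4%:

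- 2500:2500: 1.96 × √(0.0564/2500 + 0.0384/2500) = 1.21 points
- 1667:1667: 1.96 × √(0.0564/1667 + 0.0384/1667) = 1.48 points
- 4000:500: 1.96 × √(0.0564/4000 + 0.0384/500) = 1.87 points

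As an illustration, suppose 200/4000 (5%) on coflex and 20/500 (4%) on a comparator. The difference is +1.0 point and the half-width is 1.96 × √(0.0475/4000 + 0.0384/500) = 1.85 points, so the interval runs from −0.85 to +2.85 points. It includes zero, yet an excess of more than 2.5 points is not excluded. A p-value alone hides that.

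**The case against.** The strongest reply is that the plan never says complications will be tested. The sentence written for them, in 5.3, is descriptive. The primary safety objectives say assess, while measuring and comparing is reserved for the secondary objectives. The list in 4.1 proves little, because it also holds age and gender, which nobody would test for superiority. All of this stands: it cannot be said that the plan assigns Fisher's test to complications. But it only moves the gap. If 5.3 governs, a primary objective in a study titled as a comparison receives no between-group estimate.

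Second, "Fisher's exact test for superiority" may mean no more than a test of difference as opposed to non-inferiority. That is a fair reading, and the one-sided result is therefore conditional. The plan should say which is meant.

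Third, a reader might infer that real harm will often be missed. The documents do not support that. They give no rates or group sizes, and at 2500:2500 a two-sided test has 81% power or more for the doublings examined from 1% upward.

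Fourth, a reader might infer that the sponsor will present non-significance as equal safety. No section says so. The plan leaves room for that inference but does not make it.

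Finally, a crude risk difference from a non-randomised chart review is open to confounding. That is true, and equally true of Fisher's test on the same counts. It calls for a stated caveat, not for leaving out the interval.

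**Conclusion.** The point holds as a gap in specification. Adverse events are a primary objective, yet the plan leaves open whether 5.1 or 5.3 applies to complications, and no reading produces an estimate of excess harm with its uncertainty. That conclusion needs no assumption about rates. The inability of a one-sided test towards benefit to show harm is also free of such assumptions, but it applies only if the test is one-sided and 5.1 governs.

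The size under the two-sided reading depends wholly on assumed rates and splits. For 6% v 4%, misses run from about 11% to 57% across the three splits. For 1% v 0.5%, they start at about 52% in balanced groups. These figures show what can happen; they do not forecast what will. The change is worth making because it repairs all three readings at once and needs no new data.

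**What to change.** - **5.1:** Exclude complications and adverse events from the superiority rule. State sides, direction and comparison groups for the categorical outcomes that remain.
- **5.2/5.3:** For each complication type, report counts and the risk difference for coflex minus decompression alone and for coflex minus decompression with fusion, each with a two-sided 95% confidence interval. Use a score-type interval where events are few, since the simple formula above is unreliable there. Label these as non-randomised comparisons open to confounding.
- **Implant-specific events** (breakage, displacement, pain caused by the implant): report for coflex only, with an exact 95% confidence interval.
- **Interpretation:** Add a sentence that absence of statistical significance is not evidence of equal safety, and that the upper confidence limit should accompany any safety statement.

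The cost is a few sentences and some extra columns in the safety table. The downside for the sponsor is that the resulting safety statement may be less favourable than a report of no significant difference.

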Study Design	Retrospective, multi-center, post-market clinical study
Devices	coflex® Interlaminar Technology
Data Collection	Clinical, radiologic and patient reported outcomes data will be collected for approximately 5000 patients from 50 sites
Study Duration	Up to 6 months for data collection Start Date: June 2013 End Date: April 2017
Study Objectives	
Primary Objective:
 
• To assess the operative details and safety outcomes associated with the use of the coflex device• To assess post-operative adverse events• To assess post-operative follow-up duration 
Secondary Objectives:
 
• To measure and compare patient reported outcomes (e.g., VAS, Patient Satisfaction and ODI) at baseline and final follow-up• To measure and compare clinical and radiologic outcomes at baseline and final follow-up• To measure and compare the clinical, radiologic, and patient reported outcomes at interim follow-up visits• To assess the impact of demographics and risk factors on clinical, radiologic, and patient reported outcomes•
Inclusion Criteria	Patients must meet the criteria specified in the device labeling including radiographic confirmation of at least moderate lumbar stenosis, which narrows the central spinal canal at one or two contiguous levels from L1-L5 that require surgical decompression.
Exclusion Criteria	There are no exclusion criteria's for this study.

Risk/Benefit Assessment

The study is a retrospective analysis of medical records that poses no risk to the patients and minimal risk to loss of patient privacy. All results will be de-identified in the process of data review. There are no benefits to the subject as this data is being collected to obtain additional clinical evidence to support publications and marketing.

Study Abbreviations

Abbreviation	Definition
BMI	Body Mass Index
FDA	Food and Drug Administration
GCP	Good Clinical Practice
HIPAA	Health Insurance Portability and Accountability Act of 1996
ICH	International Committee on Harmonization
IRB	Institutional Review Board
MRI	Magnetic Resonance Imaging
CT	Computed Tomography
DEXA	Dual Energy X-ray Absorptiometry

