2.2 Secondary Objectives

The secondary objectives of this study are:

- To measure and compare patient reported outcomes (e.g., VAS, Patient Satisfaction and ODI) at baseline and final follow-up
- To measure and compare clinical and radiologic outcomes at baseline and final follow-up
- To measure and compare the clinical, radiologic, and patient reported outcomes at interim follow-up visits
- To assess the impact of demographics and risk factors on clinical, radiologic, and patient reported outcomes

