4.4.4 Follow-Up Visits

The following longitudinal data will be collected for all follow-up clinic visits through final follow-up:

- Work status / ADL
- Compliance with postoperative protocol/restrictions (if applicable)
- VAS (as available)
- ODI (as available)
- Patient satisfaction (as available)
- Complications
- Secondary treatments
- Narcotics use
- Diagnostic Imaging
- Incidence of Epidural Steroid Injections (ESI)

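### Section 5.1 sends every categorical outcome to Fisher's exact test for superiority; for an outcome in three or more ordered grades that test ignores the order and gives no direction

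*Combined protocol and SAP*

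**What the plan says.** Section 5.1 gives two rules. For continuous outcomes: "All continuous outcome measurements at follow-up time points will be compared to baseline values using a t-test for superiority". For categorical outcomes: "Categorical outcome measurements will be compared using a Fisher's exact test for superiority". A common threshold follows: "Statistical significance for these analyses will be demonstrated with a p-value less than 0.05". The categorical rule names no comparator, sidedness, effect measure, cut-point or method for ordered categories.

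Section 2.2 includes the objective "To measure and compare patient reported outcomes (e.g., VAS, Patient Satisfaction and ODI) at baseline and final follow-up". Section 4.1 also lists patient satisfaction, together with change in activities of daily living (ADL), among the outcomes to be assessed. Section 4.4.4 collects satisfaction at follow-up visits only where it is available. No section states the response scale of either item. The Protocol Summary says that "data will be collected for approximately 5000 patients from 50 sites". Section 5.3 says clinical outcomes will be summarised and expects them to be incomplete.

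**The concern.** Satisfaction and ADL change are often recorded in ordered grades. If they are here, Section 5.1 sends them to a test whose p-value is the same however the grades are arranged. Two things follow.

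- **Direction.** With three or more grades the test is an omnibus test of difference. It can be significant when one group has more patients at both extremes and neither group is better. Section 5.1 nevertheless attaches superiority to the result.
- **Power.** A test that ignores order spreads a consistent shift over several degrees of freedom. Collapsing to yes/no restores a direction but discards information, and with no cut fixed in advance the cut could be chosen after the data are seen.

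Because these items are collected only where available, the number analysed may be well below 5000, which is where the lost power would count.

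**Working it through.** The plan states no effect size, power or sample-size calculation, so there is no figure to reproduce. Its only usable inputs are the 0.05 threshold and the total of about 5000. Everything else below is assumed: two equal independent groups, two-sided testing, a proportional-odds shift, and the grade shares shown.

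**1. Order is ignored.** Take five grades with counts 15, 23, 30, 45, 37 against 9, 17, 26, 48, 50. The multi-category (Fisher-Freeman-Halton) test gives p = 0.32 in this order and again when the columns are shuffled. The Wilcoxon rank-sum test gives p = 0.031 in the true order and 0.94 when shuffled.

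**2. No direction.** Take 10, 30, 70, 30, 10 against 30, 30, 30, 30, 30 (150 each). Expected counts are 20, 30, 50, 30, 20, so chi-square = 4 × 10²/20 + 2 × 20²/50 = 20 + 16 = 36 on 4 df, p = 3 × 10⁻⁷. The resampled Fisher-Freeman-Halton p is about 0.00001, the smallest value that 100,000 resamples can give. With scores 1 to 5, both groups average 450/150 = 3, and Wilcoxon gives p = 1.0. The result is highly significant and neither group is better.

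**3. A binary outcome is different.** For 90/60 against 110/40, Fisher's test gives two-sided p = 0.020 and one-sided p = 0.0099 or 0.995. In a 2×2 table it does show direction.

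**4. Power.** Write p and q for the grade shares in the two groups, p̄ for their average and n for patients per group.
- Unordered test: noncentrality λ = (n/2) Σ (p − q)²/p̄ on K − 1 df, the large-sample equivalent of the multi-category exact test.
- Rank test: λ = n d²/(2v) on 1 df, where d is the difference in mean midrank score and v is the variance of that score.

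Worked case: shares 8/12/15/30/35%, odds ratio 1.5, n = 250. Dividing the cumulative odds by 1.5 gives 5.5/8.8/12.1/28.9/44.7% in the other group. For the unordered test λ = 6.16. For the rank test d = 0.0610 and v = 0.0756, so λ = 250 × 0.0610²/(2 × 0.0756) = 6.15, the same within rounding. The signal is equal; the whole loss comes from using 4 df instead of 1 (critical values 9.49 and 3.84). Power is 48% against 70%.

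The two collapsed columns are 2×2 Fisher tests simulated with 4000 replicates (standard error about 0.8 points).

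| Control shares, % | Odds ratio | n per group | Unordered, full scale | Fisher, top two grades | Fisher, top grade | Wilcoxon |
|---|---|---|---|---|---|---|
| 8/12/15/30/35 | 1.5 | 250 | 48% | 51% | 55% | 70% |
| 8/12/15/30/35 | 1.3 | 600 | 49% | 55% | 56% | 71% |
| 10/15/35/40 | 1.5 | 250 | 51% | 43% | 60% | 68% |
| 25/35/40 | 1.5 | 250 | 57% | 42% | 60% | 68% |
| 8/12/15/30/35 | 1.2 | 2500 | 83% | 85% | 87% | 95% |
| 8/12/15/30/35 | 1.3 | 2500 | 99.2% | 99.1% | 99.5% | 99.9% |

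At 250 to 600 per group the full-scale unordered test loses about 10 to 22 points (rows 4 and 1), and a collapsed Fisher test about 8 to 26 depending on the cut. Allowing for simulation error, the overall range is roughly 8 to 27.

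**5. Check with the exact test.** With four grades (10/20/35/35%), odds ratio 1.5 and 150 per group, 2000 simulated trials gave 33% for Fisher-Freeman-Halton and 48% for Wilcoxon; the formulas give the same. With no effect (five grades, 10/15/20/30/25%, 150 per group) the rejection rates were 5.1% and 4.3%.

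**6. Sample size.** For 80% power at odds ratio 1.5 the unordered test needs 412 per group against 336 with three grades (25/35/40%), and 470 against 309 with five (10/15/20/30/25%). That is 412/336 − 1 = 23% and 470/309 − 1 = 52% more.

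**The case against.** The strongest reply is that the premise is not in the documents. Satisfaction could be yes/no, where Fisher's test suits independent groups, or a numeric score, which would fall under the t-test rule. **This stands.** A reader might infer that satisfaction and ADL change are graded and will therefore lose power. The documents do not support that without the condition.

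A reader might also infer that Fisher's test is wrong for the categorical outcomes generally. It is not. Secondary surgery (Section 5.2), complications, narcotics use and steroid injections (Section 4.4.4) are naturally binary, and step 3 shows that the test can be directional there.

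The power loss is also easy to overstate. It is measured against no stated target, and all the scenarios assume a proportional-odds shift, which favours the rank test. The largest losses come from unfavourable cuts: with four grades, cutting at the top grade instead of the top two reduces the loss from 25 points to 8. A cut fixed in advance, such as satisfied or not, is a legitimate analysis and does give a direction. These points limit the size but do not restore a direction to a full-scale Fisher result.

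Section 5.3 speaks of summarising clinical outcomes, which might suggest that no test is planned. Section 2.2 still calls for comparison of patient satisfaction, and Section 5.1 is the only rule for it.

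Finally, the categorical contrast is undefined. If it is follow-up against baseline in the same patients, an unpaired ordinal test would be wrong too. This stands and shapes the fix. The groups are also not randomised, so no unadjusted test, ordinal or otherwise, would establish superiority; that is a separate matter.

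**Conclusion.** The point holds conditionally. For any outcome in three or more ordered categories, the test named in Section 5.1 ignores the order, gives no direction, and cannot by itself support superiority. That is true at any sample size and rests on no assumption beyond the scale being ordered and analysed uncollapsed.

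The power loss is illustrative: roughly 8 to 27 points at 250 to 600 per group, with the upper end tied to a poor cut. On the full scale at 2500 per group it is about 1 point or less for odds ratios of 1.3 or more, though still about 12 points at an odds ratio of 1.2 with five grades. The documents therefore do not support reading this as a study of 5000 that is underpowered for these outcomes. How much power is at stake depends on how many records carry the item, which the plan does not say.

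**What to change.** First state, for each categorical outcome, its response scale and its contrast (between groups, or follow-up against baseline). Satisfaction with surgery has no natural baseline, so its contrast needs particular care. Then amend Section 5.1 along these lines:

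> Fisher's exact test will be used for between-group comparisons of binary and unordered categorical outcomes. Outcomes with three or more ordered categories will be analysed on the full scale. Between groups, a Wilcoxon rank-sum test or a proportional-odds model will be used, the latter reporting the common odds ratio with its 95% confidence interval. For follow-up against baseline in the same patients, a paired ordinal method such as the Wilcoxon signed-rank test will be used. Any dichotomised version will use a cut-point fixed before the data are seen, or will be labelled descriptive.

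A significant Fisher result on an unordered outcome with three or more categories should be reported as a difference in distribution, not as superiority.

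The cost is wording only: no new data, patients or procedures. The one small downside is that the proportional-odds assumption must be checked where that model is used. If every item proves to be binary, the ordinal clause is never triggered and does no harm.
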